## **10.0    SAFETY REPORTING**

### **10.1    Overview and Definitions**

All adverse events associated with the DISCSS™ will be recorded and analyzed. Regulations contained in the FDA and ICH Guidelines will be followed in the identification, reporting and analysis of adverse events.

**Adverse Event:** An adverse event (AE) is any untoward medical occurrence, disease, injury, or untoward clinical signs (including abnormal laboratory findings, surgical complications, etc.), whether related or unrelated to the investigational device or its use.

**Anticipated Adverse Device Effect:** Any adverse effect related to the device, which is identified in the protocol prior to study commencement.

**Serious Adverse Event (SAE):** A Serious Adverse Event is an adverse event which:

- Led to a death,
- Resulted in life threatening illness or injury\*
- Resulted in patient hospitalization or prolongation of existing hospitalization,
- Resulted in patient disability or permanent damage or required intervention to prevent permanent impairment/damage
- Led to a congenital abnormality or birth defect

\* NOTE: the term “life-threatening” refers to an event in which the patient was at a risk of death at the time of the event; it does not refer to an event which hypothetically might have caused death if it were more severe.

**Unanticipated Adverse Device Effects (UADE):** An Unanticipated Adverse Device Effect is:

1. Any serious adverse effect on health or safety or any life threatening problem or death caused by, or associated with, a device, if that effect, problem, or death is not identified in nature, severity, or degree of incidence in this protocol; or
2. Any other unanticipated serious problem associated with a device that relates to the rights, safety, or welfare of the patients.

## 10.2 Safety Monitoring

The Sponsor/designee will monitor all adverse event reports to identify and trend all events that would require temporary discontinuation of study enrollment, to fully characterize device safety, to modify the study protocol, or to terminate the study.

## 10.3 Reporting Procedures for All Adverse Events

All adverse events occurring during the study, whether or not attributed to the DISCSS™ treatment, observed by the Investigator or reported by the participant, will be recorded on the Adverse Event CRF. After review with the participant by the study site personnel, all adverse events will be documented in the participant’s source document and on the appropriate CRF pages. The following information must be collected:

- Description of event
- Date of onset
- Date of resolution
- Duration
- Severity
- Relationship to the study device
- Action(s) taken
- Outcome(s)

The Sponsor will make the determination of whether event is anticipated or unanticipated.

The participant should be given appropriate care under medical supervision until symptoms resolve. If the adverse event is of such severity in the Investigator's judgment that it warrants withdrawal from the study, the participant should be withdrawn from treatment and the end of study evaluations should be completed and recorded on Case Report Forms.

#### **10.4 Adverse Event Severity Assessment**

Adverse events are described as mild, moderate or severe. The severity of adverse events will be assessed on the following severity index scale:

**Mild:** The adverse event is transient, requires no treatment, and does not interfere with the participant's daily activity.

**Moderate:** The adverse event introduces a low level of inconvenience or concern to the participant and may interfere with daily activities, but is usually ameliorated by simple therapeutic measures.

**Severe:** The adverse event interrupts the participant's usual daily activity and requires systematic therapy or other treatment.

#### **10.5 Relationship to Device or Procedure**

The relationship of an adverse event to the study will be graded as follows:

**None:** The adverse event is not associated with the study device use.

**Remote:** The temporal association is such that the study device is not likely to have had an association with the observed adverse event.

**Possible:** This causal relationship is assigned when the adverse event:

- a) Follows a reasonable temporal sequence from device use, but
- b) Could have been produced by the study participant's clinical state or other modes of therapy administered to the study participant.

**Probable:** This causal relationship is assigned when the adverse event:

- a) Follows a reasonable temporal sequence from device use;
- b) Abates upon discontinuation of the treatment;
- c) Cannot be reasonably explained by known characteristics of the participant's clinical state.

**Definite:** This causal relationship is assigned when the adverse event:

- a) Follows a reasonable temporal sequence from device use;
- b) Abates upon discontinuation of the treatment; and
- c) Is confirmed by the reappearance of the adverse event on repeat exposure.

#### **10.6 Timelines for Adverse Event Reporting**

Adverse events shall be recorded in the patient's study records and in the EDC on the Adverse Event eCRF within 72 hours of the site becoming aware of the event. The study database will be configured to notify the Sponsor of all adverse events that are indicated to be 'serious'. Serious adverse events (SAEs) will trigger the database to send an email notification to the Sponsor using the contact information provided below.

Sponsor Contact: [name]  
E-mail: [[contact]](mailto:[contact])  
E-mail: [[contact]](mailto:[contact])

The Investigator should provide additional information on the SAE by updating the information on the Adverse Event eCRF as updates become available. The Sponsor may also ask for additional clinical reports including redacted source documents to be provided by the Investigator to assist in the assessment of the event. Significant new information and updates should continue to be submitted promptly to the Sponsor and entered on the Adverse Event eCRF as they become available, and the Investigator should follow the SAE until it is resolved or no further improvement is expected.

The Sponsor shall ensure that the Investigator submits safety event notifications to the governing Investigational Review Board (IRB) within the timeframe specified by the IRB, when applicable. Acceptable means of confirming that the IRB requirements have been met include forwarding a copy of the written, signed report that was sent to the IRB to the Sponsor. Copies of this report should be filed in the Investigator's site files and the Sponsor's clinical investigation files.

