## **11.0 Protocol Deviations**

A protocol deviation is any noncompliance with the clinical protocol or Good Clinical Practice Guidelines. The noncompliance may be either on the part of the participant, the Investigator, or the study site staff. The site must record all protocol deviations with an explanation for the deviation on the appropriate study forms. If required, deviations will be reported to the IRB per the IRB's guidelines.

***Minor Deviations:*** A minor deviation does not impact the participants' rights, safety, or well-being, or the completeness, accuracy or reliability of the study data. Minor deviations shall be documented in the study database along with a full description of the event and outcome. The Sponsor will analyze these deviations and assess their significance. Minor deviations should be reported to the reviewing IRB if required by the IRB's deviation reporting guidelines.

***Major deviations:*** A major deviation is a deviation from the protocol that may impact the participants' rights, safety, or well-being, or the completeness, accuracy or reliability of the study data, or a deviation from FDA regulations or IRB guidelines. Major deviations should be reported to the Sponsor within 24 hours of site awareness of the event and must be documented in the study database along with a full description of the event and outcome. The Sponsor will analyze these deviations and assess their significance. Major deviations should be reported to the reviewing IRB per the IRB's deviation reporting guidelines.

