### **13.2 Regulatory Considerations**

This study will be conducted in accordance with the Good Clinical Practice (GCP) guidelines and applicable regulatory requirements (FR, ICH, E3-E6 ISO14155) including but not limited to:

- The Food and Drug Administration (FDA) Regulations on Investigational Device Exemption (21 CFR 812),
- The FDA Regulations on research with human beings (21 CFR 50 and 56),
- The Health and Human Services (DHHS) Regulations on research with human beings (45 CFR 46 Subparts A, B, C, and D) and
- The International Conference on Harmonization (ICH) "Guidance for Industry-E6 Good Clinical Practice: Consolidated Guideline."

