### **13.3 Informed Consent**

The Informed Consent Form (ICF) for this study will be prepared in accordance with FDA 21 CFR Part 50. The ICF will be used to explain the possible risks and benefits to the patient in simple terms before the patient is entered into the study. The ICF will contain a statement that the consent is freely given, that the patient is aware of the risks and benefits of entering the study, and that the patient is free to withdraw from the study at any time. The ICF will need to be reviewed and approved by the Sponsor or its designee prior to the IRB/EC submission. All appropriate bills/ legislative actions are to be considered and the ICF amended, as appropriate (e.g. California Bill of Rights is to be on the forefront of the ICF if study conducted in California).

Prior to a patient's participation in the study, the written ICF will be signed and personally dated by the patient or by the patient's legally acceptable representative, and witnessed by the person who conducted the informed consent discussion. If a patient is unable to read or if a legally acceptable representative is unable to read, an impartial

witness will be present during the entire consent discussion. After the written ICF and any other written information to be provided to the patient is read and explained to the patient or legal representative, and oral consent to the patient's participation in the study has been given by the patient, the witness will sign and date the ICF.

The Investigator must document acquisition of patient consent in the patient's medical records, and the patient or legal representative must be given a copy of the ICF document prior to enrollment into the study.

The Investigator is required to report any failure to obtain patient consent to the IRB/EC and the Sponsor or its designee, within 24 hours of learning of such an event.

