#### **14.0 CLINICAL MONITORING**

The Sponsor's Clinical designee (the CRO) will perform the clinical study monitoring. The CRO's staff will be trained and have the scientific and clinical knowledge needed to monitor the study appropriately.

Monitoring will include pre-investigational site Visits (Site Qualification Visit and Site Initiation Visit), Interim Monitoring Visits and a Close-out Visit. Monitoring will occur as frequently as needed to assure proper conduct of the protocol.

Interim Monitoring visits will be performed as frequently as needed in order to assure appropriate study implementation. Monitoring visits will be documented on monitoring visit reports, and will aim to verify that:

- Compliance with the clinical protocol and applicable regulations is being maintained
- Only authorized site individuals are participating in study activities
- The investigational device is being used according to the protocol and instructions for use
- Adequacy of staffing and facilities
- Adequate access of site to eligible patients
- Signed and dated informed consent forms have been obtained from each patient
- eCRFs and queries are complete
- Source data is verified and signed-off upon as accurate
- Patient files are accurate and complete
- All adverse events are reported to the Sponsor
- All serious and unanticipated adverse device events are reported to the Sponsor and the IRB/EC
- All other required reports, notifications, applications, submissions, and correspondence are maintained in the Investigator's files and are accurate
- Maintenance and calibration of equipment relevant to clinical assessments is appropriately performed and documented
- Patient withdrawal has been documented (if applicable)
- Patient non-compliance has been documented (if applicable)
- The Investigator and site staff are informed and knowledgeable of all relevant document updates concerning the clinical investigation
- Corrective and preventive actions have been implemented (if applicable)

Each site's Investigator will allocate adequate time for monitoring activities. The Investigator will also ensure that the monitor or other compliance or quality assurance reviewer is given access to the study-related documents and study related facilities, and has adequate space to conduct the monitoring visit.

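### Section 10.6 lets first notice of a serious adverse event to the sponsor take up to 72 hours, while major deviations and consent failures must be reported within 24

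*Protocol*

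**What the plan says.** Protocol Section 10.6 fixes a single time limit for adverse events. They go into the study records and are entered "on the Adverse Event eCRF within 72 hours of the site becoming aware of the event". Serious events have no separate limit. On how the sponsor learns of them, the section says: "Serious adverse events (SAEs) will trigger the database to send an email notification to the Sponsor". The e-mail is sent only for an event that the site has entered and marked as serious.

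For what follows the first report, Section 10.6 adds: "Significant new information and updates should continue to be submitted promptly to the Sponsor".

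Two other sections give the sponsor a faster notice. Section 11.0 states: "Major deviations should be reported to the Sponsor within 24 hours of site awareness of the event". Section 13.3 requires a failure to obtain consent to be reported "to the IRB/EC and the Sponsor or its designee, within 24 hours of learning of such an event".

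**The concern.** The section headed as the timeline for adverse event reporting treats a death or a life-threatening injury, both SAEs under Section 10.1, like a mild and transient complaint. A deviation that touches only the completeness of the data is a major deviation under Section 11.0 and has a 24-hour limit. An SAE is not in itself a deviation, so it does not inherit that limit.

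The investigator can treat the affected participant at once, so that person's care does not depend on the notice. The study-level decisions do depend on it, because they rest with the sponsor:

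- identifying events that call for a pause in enrolment (Section 10.2);
- judging whether an SAE is an unanticipated adverse device effect (UADE), and sending the resulting report to all investigators (Section 10.7);
- deciding, with the investigators, whether the risk is unreasonable and the study must end (Section 10.8).

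The study runs at 5–7 centers (Section 3.1). Every site other than the reporting one depends on the sponsor for this information.

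**Working it through.** **Step 1: is a shorter first-notice time for SAEs stated anywhere?**

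| Place | What it covers | Time limit for first SAE notice to the sponsor |
|---|---|---|
| 10.6, entry rule | all adverse events | 72 h from site awareness |
| 10.6, database e-mail | events marked serious | none of its own; follows entry |
| 10.6, updates | new information after the first report | none; prompt submission applies to updates only |
| 10.6, IRB reports | notice to the IRB | none; the IRB's timeframe governs the IRB only |
| 10.3 | what to record | none |
| 14.0 | monitors check that "All serious and unanticipated adverse device events are reported to the Sponsor and the IRB/EC" | none |
| 10.1 and 13.2 | general reference to FDA, ICH and ISO rules | none printed |

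Sections 4.3, 6.5 to 6.8 and 8.9 give no such limit either. The longest delay open to a compliant site is therefore 72 h, assuming that the e-mail leaves as soon as the event is entered and marked serious. An event not marked serious at entry triggers no e-mail.

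**Step 2: comparison with the other clocks.** Inputs: 72 h (10.6) and 24 h (11.0 and 13.3).

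- Ratio: 72 / 24 = 3
- Difference: 72 − 24 = 48 h

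**Step 3: comparison with the length of exposure.** Visit 5 comes 3–4 days after Visit 4 (Section 6.6), so exposure lasts 3 × 24 = 72 h to 4 × 24 = 96 h.

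| Time to notice | Share of a 4-day exposure | Share of a 3-day exposure |
|---|---|---|
| 72 h | 72/96 = 75% | 72/72 = 100% |
| 24 h | 24/96 = 25% | 24/72 = 33% |
| extra 48 h | 48/96 = 50% | 48/72 = 67% |

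So a participant who starts the device at another site when the first site learns of an SAE could finish a 3-day exposure before the sponsor hears of it.

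**Step 4: what runs after notice.** The 10-working-day limit for the UADE report to FDA (Section 10.7) counts from the sponsor's first notice, so the site's time comes on top of it. The 5 working days in Section 10.8 for termination procedures also belong to the sponsor's stage, after it knows of the event. The shares in Step 3 measure time to notice, not time to action.

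**The case against.** The strongest reply has four parts.

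- **Nothing contradicts anything.** The 24-hour clocks apply to two kinds of compliance event, not to clinical safety data, so there is no general 24-hour standard that SAEs break. This stands as far as it goes. The point is one of priority between sections, and it does not need a general standard.
- **Outside rules may already shorten the time.** Section 10.1 says that "Regulations contained in the FDA and ICH Guidelines will be followed in the identification, reporting and analysis of adverse events", and Section 13.2 adds further regulations and standards. Incorporation by reference is legitimate, and the content of those rules cannot be checked here. But site staff will work to the number that the protocol prints, and the only one printed for an adverse event is 72.
- **The sponsor's own limits are longer than the saving.** Five working days is at least 5 × 24 = 120 h. Even with notice at 24 h, the outer limit for termination procedures is 24 + 120 = 144 h, beyond the longest exposure of 96 h. This is fair for a sponsor that uses its full allowance. But those limits are ceilings, Section 10.2 states no waiting time for a pause in enrolment, and earlier notice helps a sponsor that acts sooner.
- **Exposure shares do not measure harm.** The useful figure would be the number of other participants exposed during the extra 48 h. This also stands. The protocol gives no enrolment rate and no SAE rate, so that number cannot be derived. The shares only put the delay on the scale of a very short treatment.

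**Conclusion.** The concern holds. Section 10.6 is a stated rule, not a detail left open, and a site that follows it exactly can delay the sponsor's first knowledge of an SAE by up to 48 hours more than for a major deviation or consent failure. Seventy-two hours is a ceiling, and a site may enter an SAE sooner. The practical effect is modest, and it arises only when an SAE leads the sponsor to act. No endpoint or estimate is affected. The change is still worth making, because it speeds the sponsor's safety oversight at very low cost. The conclusion assumes that the e-mail is sent immediately on entry and that no unseen site instruction sets a shorter time.

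**What to change.** Add one sentence to Section 10.6: SAEs must be entered in the EDC, or otherwise notified to the sponsor, within 24 hours of site awareness. Keep the 72-hour entry limit for non-serious events. This matches the notice that Sections 11.0 and 13.3 already ask of sites.

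The cost is that sentence and a line in site training. Sites carry a small extra burden, and first SAE reports may be less complete; the update rule already in Section 10.6 handles that. No new category of reportable event is created.

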## **10.7 Determination and Reporting of Unanticipated Adverse Device Effects**

The Sponsor shall review all reported SAEs to evaluate whether they meet the criteria for an Unanticipated Adverse Device Effect. For adverse events that are determined to be UADEs, the Sponsor will submit an expedited safety report to the FDA's Center for Devices and Radiological Health (CDRH). The expedited safety report will consist of a completed Form FDA 3500A and a cover letter analyzing the significance of the event. The expedited safety report will be submitted to the FDA as soon as possible and, in no event, later than 10 working days after the Sponsor first receives notice of the UADE. A copy of this safety report will be provided to all participating study Investigators.

If, following receipt and investigation of follow-up information regarding an adverse event that was previously determined not to be a UADE, the Sponsor determines that the event does meet the requirements for expedited reporting, the Sponsor will submit a completed Form FDA 3500A and cover letter as soon as possible, but in no event later than 10 working days after this is determined.

## **10.8 Study Termination**

The Sponsor, in consultation with the Investigators, shall determine if the reported event presents an unreasonable risk to study patients. If the event is determined to pose an unreasonable risk, the Sponsor shall develop procedures to terminate the study within 5 working days.

## **10.9 Treatment of Adverse Events**

Adverse events that occur during the study shall be handled by established standards of care to protect the health and safety of the patient. Necessary care shall be provided by the Investigator or designee.

## **11.0 Protocol Deviations**

A protocol deviation is any noncompliance with the clinical protocol or Good Clinical Practice Guidelines. The noncompliance may be either on the part of the participant, the Investigator, or the study site staff. The site must record all protocol deviations with an explanation for the deviation on the appropriate study forms. If required, deviations will be reported to the IRB per the IRB's guidelines.

***Minor Deviations:*** A minor deviation does not impact the participants' rights, safety, or well-being, or the completeness, accuracy or reliability of the study data. Minor deviations shall be documented in the study database along with a full description of the event and outcome. The Sponsor will analyze these deviations and assess their significance. Minor deviations should be reported to the reviewing IRB if required by the IRB's deviation reporting guidelines.

***Major deviations:*** A major deviation is a deviation from the protocol that may impact the participants' rights, safety, or well-being, or the completeness, accuracy or reliability of the study data, or a deviation from FDA regulations or IRB guidelines. Major deviations should be reported to the Sponsor within 24 hours of site awareness of the event and must be documented in the study database along with a full description of the event and outcome. The Sponsor will analyze these deviations and assess their significance. Major deviations should be reported to the reviewing IRB per the IRB's deviation reporting guidelines.

## **12.0 STATISTICAL CONSIDERATIONS**

For this feasibility study, descriptive statistics will be utilized to describe the data for each endpoint. For continuous variables, this include the mean value, change from baseline, standard deviation, and 95% confidence interval. For categorical variables, the rate and a 95% confidence interval will be presented. As there is no comparator group for this clinical study, no hypothesis-based statistical testing is planned. For adverse event information, the

number of events, the number of subjects experiencing events, and the rate of subjects experiencing an event will be presented.

